7.4.5.2 Medications and Treatments Prohibited During the Study

Subjects will be advised to avoid the following for the duration of the study:

- Facial plastic surgery or permanent facial implants (e.g., polymethylmethacrylate, silicone, polytetrafluoroethylene, polyacrylamide, lifting threads) anywhere in the face or neck
- Semi-permanent dermal filler treatment (e.g., calcium hydroxylapatite, poly-L-lactic acid) in the lower face (below the orbital rim)

- Other hyaluronic acid filler materials or collagen-based filler materials below the orbital rim
- Facial tissue augmentation with fat injections, botulinum toxin injections in the lower face (below the orbital rim), mesotherapy, or cosmetic procedures in the face or neck (e.g., face-lift, laser, photo-modulation, intense pulsed light, radio frequency, dermabrasion, moderate or greater depth chemical peel, microneedling, or other ablative procedures)
- Use of any lip plumping products or devices
- Use of any OTC or prescription, oral or topical, anti-wrinkle products for the lips or around the mouth (Subjects who have been on a regimen of such products for at least 90 days must continue their regimen throughout the study.)

7.4.5.3 Concomitant Medications and Treatments Allowed During the Study

Permitted medications/treatments include any concomitant medication/treatment not listed below.

- Facial plastic surgery or permanent facial implants (e.g., polymethylmethacrylate, silicone, polytetrafluoroethylene, polyacrylamide, lifting threads) anywhere in the face or neck
- Semi-permanent dermal filler treatment (e.g., calcium hydroxylapatite, poly-L-lactic acid) in the lower face (below the orbital rim)
- Facial tissue augmentation with fat injections, botulinum toxin injections in the lower face (below the orbital rim), mesotherapy, or cosmetic procedures in the face or neck (e.g., face-lift, laser, photo-modulation, intense pulsed light, radio frequency, dermabrasion, moderate or greater depth chemical peel, microneedling, or other ablative procedures)
- Use of any lip plumping products or devices
- Use of any OTC or prescription oral or topical anti-wrinkle products for the lips or around the mouth (Subjects who have been on a stable regimen of such products for at least 90 days must continue their regimen throughout the study.)

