7.3.3 Subject Withdrawal Criteria

A subject may withdraw from the study at any time for any reason.

A subject will be withdrawn from the study if his/her safety or well-being is determined to be at risk. Withdrawal will be made at the discretion of the investigator or at the subject's request.

A subject must withdraw from the study for any of the following reasons:

- The subject or legal representative withdraws consent
- There is a significant protocol violation as determined by the Sponsor or medical monitor.

A subject may be withdrawn from the study for any of the following reasons:

- Lost to follow-up
- Investigator discretion

Withdrawal is permanent; after a subject has been withdrawn, he/she will not be allowed to enroll again.

If a subject is withdrawn from the study for any reason, the EOS or Early Termination procedures (Visit 3/Month 2) should be completed and any outstanding data and study device should be collected. Data, including the date and primary reason for withdrawal, must be documented on the EOS case report form (CRF) and source document.

If a subject withdraws from the study at any time due to an AE, the reason for withdrawal, the nature of the AE, and its clinical course must be fully documented. The investigator must strive to follow the subject until the AE has resolved, become clinically insignificant, is stabilized, or the subject is lost to follow-up. For any SAE, follow procedures provided in Section 7.9.7.

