7.6.6 Concomitant Medication/Treatment Review

Concomitant medications (including prescription, OTC, and dietary supplements taken and other treatments and cosmetic products used by the subject) will be reviewed with the subject at each study visit and telephone contact.

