7.7.1 Visit 1/Day 1: Treatment

This is the same as Visit 5 of Protocol PRO 2018-02 and assessments performed for that study (e.g., LFGS and POL assessments) do not need to be repeated for this study.

- Obtain written informed consent
- Evaluate inclusion/exclusion criteria
- Update the medical history and demographic information as needed from that at entry to Protocol 2018-02
- Perform vital signs (temperature, heart rate, blood pressure, and respiratory rate)
- Vision evaluation (Snellen visual acuity, confrontational visual fields, ocular motility)
- Obtain/record concomitant medications/treatments
- Perform urine pregnancy test for all women of childbearing potential
- LFGS assessment
- POL assessment
- Lip function evaluation prior to treatment administration
- Lip sensation evaluation prior to treatment administration

- Lip texture evaluation prior to treatment administration
- Lip firmness evaluation prior to treatment administration
- Lip symmetry evaluation prior to treatment administration
- Lip movement/function prior to treatment administration
- Treatment administration
- Vision evaluation (Snellen visual acuity, confrontational visual fields, ocular motility)
- Investigator Ease of Use assessment
- Assess AEs
- Dispense subject diary card
- Schedule next visit
- Complete CRFs

7.7.2 Telephone Contacts on Day 3 and Day 14

- Assess AEs
- Assess concomitant medications/treatments
- Confirm adherence to prohibited treatments/medications

7.7.3 Visit 2/Day 28 (± 2 days): Month 1

- LFGS assessment
- POL assessment
- pGAI assessment
- iGAI assessment
- Lip function evaluation
- Lip sensation evaluation
- Lip texture evaluation
- Lip firmness evaluation
- Lip symmetry evaluation
- Lip movement/function
- Vision evaluation (Snellen visual acuity, confrontational visual fields, ocular motility)
- Assess AEs
- Swelling assessment
- Assess concomitant medications/treatments
- Subject satisfaction with lips (VAS)

- Complete CRFs

7.7.4 Visit 3/Day 56 (\pm 4 days): Month 2 End of Study Visit/Early Termination

- LFGS assessment
- POL assessment
- pGAI assessment
- iGAI assessment
- Lip function evaluation
- Lip sensation evaluation
- Lip texture evaluation
- Lip firmness evaluation
- Lip symmetry evaluation
- Lip movement/function
- Vision evaluation (Snellen visual acuity, confrontational visual fields, ocular motility)
- Assess AEs
- Swelling assessment
- Assess concomitant medications/treatments
- Subject satisfaction with lips (VAS)

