7.7.6 Unscheduled Visit

An unscheduled visit is allowed at any time if in the investigator's opinion it is warranted. The following procedures may be performed at the Unscheduled Visit if required.

- LFGS assessment
- POL assessment
- pGAI assessment
- iGAI assessment
- Lip function evaluation
- Lip sensation evaluation

- Lip texture evaluation
- Lip firmness evaluation
- Lip symmetry evaluation
- Lip movement/function
- Vision evaluation (Snellen visual acuity, confrontational visual fields, ocular motility)
- Assess AEs
- Swelling assessment
- Subject satisfaction with lips (VAS)
- Assess concomitant medications/treatments
- Complete CRFs

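### Protocol 7.4.5.2 prohibits other hyaluronic acid and collagen-based fillers below the orbital rim, while 7.4.5.3 permits them by leaving them off its own list

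*Protocol*

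**What the plan says.** Section 7.4.5.2 of the protocol, whose heading labels its content as prohibited, has six bullets. The third reads "Other hyaluronic acid filler materials or collagen-based filler materials below the orbital rim".

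Section 7.4.5.3, on what is allowed, works by exclusion: "Permitted medications/treatments include any concomitant medication/treatment not listed below". Five bullets follow. None names hyaluronic acid or collagen.

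Both sections close with an exception for anti-wrinkle products. In 7.4.5.2 it reads "Subjects who have been on a regimen of such products for at least 90 days must continue their regimen throughout the study"; in 7.4.5.3 it reads "Subjects who have been on a stable regimen of such products for at least 90 days must continue their regimen throughout the study".

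The rule is used elsewhere. The telephone contacts on Days 3 and 14 (Section 7.7.2) and Day 168 (Section 7.7.5) include the task "Confirm adherence to prohibited treatments/medications". Section 7.3.3 makes withdrawal mandatory when "There is a significant protocol violation as determined by the Sponsor or medical monitor".

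**The concern.** A site that follows 7.4.5.2 would record another hyaluronic acid or collagen-based filler as a prohibited treatment. A site that follows 7.4.5.3 could record the same event as permitted. Each could cite the protocol. The adherence check and the judgement on protocol violations both work better with one rule.

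The omitted class is also the one most likely to matter to the scores. PN40082 is a hyaluronic acid gel, and another filler of that class in the lip or perioral area could move the lip fullness (LFGS), perioral line (POL) and global aesthetic improvement (pGAI, iGAI) ratings. The study has no concurrent control, SAP Section 4 analyses all retreated subjects, and the SAP has no rule for scores recorded after such a treatment. A change due to another filler could therefore be read as an effect of retreatment.

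**Working it through.** No arithmetic beyond counting applies. The two lists compare as follows.

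| Item | 7.4.5.2 (prohibited) | 7.4.5.3 (not permitted) |
|---|---|---|
| Facial plastic surgery, permanent implants | listed | listed |
| Semi-permanent fillers, lower face | listed | listed |
| Other hyaluronic acid or collagen-based fillers below the orbital rim | listed | **absent** |
| Fat, botulinum toxin, mesotherapy, cosmetic procedures | listed | listed |
| Lip plumping products or devices | listed | listed |
| Anti-wrinkle products, with a 90-day exception | listed | listed, exception worded differently |

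**Counts.** There are 6 items in the first list and 5 in the second, so 6 − 5 = 1 is missing. Of the 5 shared items, 1 differs: its exception requires a regimen in one section and a stable regimen in the other.

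**Could another bullet in 7.4.5.3 cover the missing class?** Three candidates were considered.

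- *Semi-permanent fillers.* The examples are calcium hydroxylapatite and poly-L-lactic acid. Section 7.4.5.2 has the same bullet and still lists hyaluronic acid and collagen separately.
- *Cosmetic procedures in the face or neck.* The examples are surgical, energy-based or ablative. Section 7.4.5.2 has the same wording and again lists the fillers separately.
- *Lip plumping products or devices.* This too appears in both sections, and at most it would reach the lips, not the whole area below the orbital rim.

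The protocol's own drafting therefore treats hyaluronic acid and collagen fillers as a class apart, and no other bullet fills the gap.

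**Is there a precedence rule?** Section 7.4.5.3 does not refer back to 7.4.5.2, and no text elsewhere in the protocol or SAP ranks the two lists.

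**Where is the rule checked?** There are five scheduled post-treatment contacts: Days 3, 14, 28, 56 and 168. Adherence to the prohibitions is named as a task at 3 of the 5, all of them telephone calls. Visits 2 and 3 (Days 28 and 56), where the scores are taken, list only the general concomitant treatment review. Section 7.6.6 does require that "other treatments and cosmetic products used by the subject) will be reviewed with the subject at each study visit and telephone contact", so such use should be recorded at all five contacts. What is unclear is how it is classified.

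**The case against.** The strongest reply is that few readers would be misled. An express prohibition of a named class normally outweighs a general clause allowing whatever is not listed. The adherence check uses the word prohibited, which is the label on 7.4.5.2. The near-verbatim overlap suggests a copying slip. Withdrawal for a significant violation is decided by the sponsor or medical monitor, so differing site readings would not settle it on their own. This has force and keeps the point minor. It does not remove the contradiction: 7.4.5.3 is an open-ended permission with its own exception list, and a likely intention is not the same as consistent text.

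A second reply is that another filler before a scored visit would disturb an uncontrolled score whether or not it was permitted. That is correct. Reconciling the lists bears on how likely such use is and how it is classified, not on the size of any disturbance.

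Third, some supporting details are slight. The 3-of-5 count describes where the rule is checked and does not measure the mismatch, and the Day 168 call comes after the last scheduled scored visit. Section 7.7.6 says "An unscheduled visit is allowed at any time" and lets the scales be repeated then, but the efficacy table shells show only Visits 1, 2 and 3. The difference between a regimen and a stable regimen is small, since both versions require at least 90 days and continued use.

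**Conclusion.** The inconsistency is real and stands on the face of the text: 1 of 6 prohibited items is missing from a list that permits everything it does not name, and 1 of the 5 shared items has different exception wording. It is minor. SAP Section 5.1 rules out inferential analysis, so no test, error rate or decision rule is affected. The documents do not say how often subjects receive other fillers, so no effect on the ratings is claimed.

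The conclusion rests on a literal reading of 7.4.5.3 and on the absence of any text ranking the two sections. It takes no position on which clinical rule should apply.

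**What to change.** Reconcile Sections 7.4.5.2 and 7.4.5.3 so that both give the same list and the same exception wording, for instance through a single list that both sections refer to. Which treatments belong on it is for the sponsor to decide. Section 7.4.5.1 is worth reading in the same pass: it tells subjects to avoid epilation and chemical peeling, whereas 7.4.5.3 does not name epilation and names chemical peels only from moderate depth upward.

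Optionally, Listings 16.2.6.1 and 16.2.6.2 could flag any score recorded after a treatment on the reconciled list. Treatment dates are already planned in Listings 16.2.4.4 and 16.2.4.5. The two efficacy listings have no date column, so visit dates would come from Listing 16.2.1.2. The efficacy tables and the use of all available data need not change.

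The main cost is one wording correction across two sections. Protocol Section 10.5 requires documented sponsor and IRB approval for a revision, so the correction can go in with the next one, with a written clarification to sites beforehand if useful. The flag would add one column to each of two listings, which SAP Section 6 already allows, and needs no new data collection.

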7.4.6 Assessment of Compliance

Administration of the study device by the investigator is documented on the CRF.

7.5 Study Schedule

The visit-by-visit schedule of study activities is provided in Section 2. The timing of each visit is relative to Day 1, which is defined as the day the subject is treated in the present open-label study.

All visits should be performed within the windows specified on the schedule of study activities. Every attempt should be made to have each subject attend each visit as scheduled. If a subject is unable to attend a visit within the specified window the visit should be scheduled as closely as possible to the applicable window.

7.6 Study Procedures

The schedule of study activities summarizes the study procedures to be performed at each visit. Individual study procedures are described below.

All clinical assessments (LFGS, POL, iGAI, lip function, lip sensation, lip texture, lip firmness, lip symmetry, and lip movement/function evaluations) must be conducted by qualified investigators listed on Form FDA 1572 who have been delegated these tasks by the principal investigator (PI). The PI may delegate this task only to physicians, physician assistants, or nurse practitioners who have documented training for this protocol and past experience conducting the assessment.

To minimize variability of evaluations, the same investigator/sub-investigator should perform these assessments for any given subject and anticipate evaluating the subject at each visit, to the extent possible.

7.6.1 Study Roles

As this is an open-label study, there is no distinction between treating and evaluating investigators.

7.6.2 Written Informed Consent

The study personnel will review the ICF for this study with each subject and give the subject an opportunity to have all questions answered before proceeding with any study procedures. A copy of the signed ICF will be given to every subject and the original will be maintained with the subject's records.

7.6.3 Significant Medical History/Demographic Information

Medical history and demographic information will be updated if/as needed at Visit 1/Day 1 to record any changes since Visit 1 in Protocol PRO 2018-02.

7.6.4 Vital Signs

Vital signs will be recorded. Vital signs will include sitting blood pressure, temperature, heart rate, and respiratory rate.

7.6.5 Vision Evaluations

Subjects will be assessed with Snellen visual acuity, confrontational visual fields, and ocular motility by a trained evaluator. These assessments will be performed at Visit 1/Day 1 prior to treatment and repeated 30 minutes following treatment and at Visit 2/Month 1 and Visit 3/Month 2.

7.6.6 Concomitant Medication/Treatment Review

Concomitant medications (including prescription, OTC, and dietary supplements taken and other treatments and cosmetic products used by the subject) will be reviewed with the subject at each study visit and telephone contact.

7.6.7 Urine Pregnancy Test and Acceptable Contraceptive Methods

Women of childbearing potential, in addition to having a negative urine pregnancy test at Visit 1/Day 1, must be willing to use an acceptable form of birth control during the study. The following are considered acceptable methods of birth control for the purpose of this study: oral contraceptives, contraceptive patches, contraceptive implant, vaginal contraceptive, double barrier methods (e.g., condom and spermicide), contraceptive injection (Depo-Provera[®]), IUD, hormonal IUD (Mirena[®]), and abstinence with a documented second acceptable method of birth control if the subject becomes sexually active. Subjects entering the study who are on hormonal contraceptives must have been on the method for at least 90 days prior to the study and continue the method for the duration of the study. Subjects who had used hormonal contraception and stopped must have stopped no less than 90 days prior to Visit 1/Day 1.

7.6.8 Lip Fullness Grading Scale

The LFGS is a validated 5-point photonumeric rating scale that was developed to objectively quantify the 3-dimensional fullness of the lip. The scale ratings are 0 for very thin, 1 for thin, 2 for moderately thick, 3 for thick, and 4 for full (Carruthers et al, 2008). Photographs illustrating the ratings will be provided to each site. The assessments of overall lip fullness considering both lips together, fullness of the upper lip, and fullness of the lower lip will be performed at each study visit.

7.6.9 Perioral Lines at Rest Severity Scale

The POL is a 4-point rating scale that corresponds to the most severe perioral line attribute when the subject's mouth is at rest with the following ratings (Cohen et al, 2014):

0. None – a mouth with no perioral lines
1. Mild – a mouth with a few shallow perioral lines
2. Moderate – a mouth with some moderate lines
3. Severe – a mouth with many deep lines or crevices

The assessments of overall perioral lines at rest severity considering both lips together, perioral lines at rest severity of the upper lip, and perioral lines at rest severity of the lower lip will be performed at each study visit.

7.6.10 Review Inclusion/Exclusion Criteria

The inclusion and exclusion criteria will be reviewed by the investigator or qualified designee to ensure that the subject qualifies for the study.

7.6.11 Patient Global Aesthetic Improvement (pGAI) Score

The pGAI score is a 5-point scale with the following categories:

1. Worse – the appearance is worse than the original condition.
2. No change – the appearance is the same as the original condition.
3. Improved – obvious improvement in appearance from the initial condition. A touch-up might further improve the result.

4. Much improved – marked improvement in appearance from the initial condition, but not completely optimal. A touch-up might slightly improve the result.
5. Very much improved – optimal cosmetic result.

The pGAI score will be recorded at Visit 2/Month 1 and Visit 3/Month 2. Subjects will be asked the question “How would you rate improvement in your appearance compared to your initial condition using the scale below?”

7.6.12 Investigator Global Aesthetic Improvement (iGAI) Score

The iGAI score is a 5-point scale with the following categories:

1. Worse – the appearance is worse than the original condition.
2. No change – the appearance is the same as the original condition.
3. Improved – obvious improvement in appearance from the initial condition. A touch-up might further improve the result.
4. Much improved – marked improvement in appearance from the initial condition, but not completely optimal. A touch-up might slightly improve the result.
5. Very much improved – optimal cosmetic result.

The iGAI score will be assessed at Visit 2/Month 1 and Visit 3/Month 2.

7.6.13 Investigator Ease of Use Assessment

The Treating Investigator will assess overall ease of use by the device by circling the appropriate number on the numerical rating scale from 0 being not easy to 10 being most easy at Visit 1/Day 1.

7.6.14 Swelling Assessment

Swelling will be assessed by the Investigator at Visit 2/Month 1 and Visit 3/Month 2 using the 5-point scale with the categories that follow. The Investigator should examine both upper and lower lip simultaneously and recall the degree of augmentation originally provided for comparison. The subject should not be specifically questioned regarding swelling but if the subject spontaneously reports it, such information can be used to assist in selection of a grade for swelling.

0. None – No swelling noticeable. Lips appear the same as when originally augmented. Any lip enlargement is due to the implanted product only.
1. Minimal – Slight enlargement of either lip beyond the originally provided augmentation. May or may not be noticeable to the subject but is noticeable to the investigator.
2. Mild – Some enlargement of either lip beyond the original augmentation that is easily noticeable to the subject, but the lips do not appear abnormally large.
3. Moderate – Significant enlargement of either lip beyond the original augmentation. Either lip appears abnormally large.

4. Severe – Any degree of swelling that substantially interferes with lip function such as changes in speech or difficulty eating or drinking.

7.6.15 Lip Function Evaluation

Lip function will be assessed by the Investigator by the subject’s ability to sip liquid through a straw prior to treatment at Visit 1/Day 1 and at Visit 2/Month 1 and Visit 3/Month 2.

7.6.16 Lip Sensation Evaluation

Lip sensation will be assessed by the Investigator and tested via: 1) the monofilament test (a subject’s ability to feel the sensation of a 0.4G monofilament at 3 points on the upper lip and 3 points on the lower lip, and 2) the cotton wisp test (a subject’s ability to feel the sensation of a cotton wisp at 3 points on the upper lip and 3 points on the lower lip) prior to treatment at Visit 1/Day 1 and at Visit 2/Month 1 and Visit 3/Month 2.

